
$$LEI = n \times \frac{\sum_{i=1}^n score}{\sum_{i=1}^n AI}$$

Note that n here refers to the number of total items.

Enthesitis-free state is based on a LEI response of 0 at Week 16, for subjects with enthesitis at Baseline (LEI>0).

Enthesitis-free state at Week 16 (pooled between PA0010 and PA0011) is the 7th endpoint in the sequential testing hierarchy (Table 4-5) and will be based on pooled data from PA0010 and PA0011 (for subjects in the BKZ160mg Q4W and the Placebo groups). The analysis will also be repeated using PA0010 data alone and the p-value for this analysis will only be considered nominal.

8.2.1.7 Dactylitis-free state at Week 16 in the subgroup of subjects with dactylitis at Baseline

The LDI measures the percent difference between the circumference of the affected digit and the circumference of the digit on the opposite hand or foot (referred to as the contralateral digit), where circumference is measured in millimeters. A minimum difference of 10% and the assessment of the investigator that the digit was affected by dactylitis will be used to define a dactylitis digit.

The percent difference between circumferences will be multiplied by a tenderness score (0 for non-tender, 1 for tender). The score using the binary tenderness score is referred to as the LDI basic. The results from each digit with dactylitis will then be summed to produce a final LDI score.

Table 8-3 is a table of normative values, which will be used to provide the comparison, if matching digits are thought to be involved.

Table 8-3: Normative values for LDI

	Digit	Men	Women
Hand	Thumb	70	58
	Index	63	54
	Middle	63	54
	Ring	59	50
	Little	52	44
Foot	Great toe	82	72

	Digit	Men	Women
	Second	52	46
	Middle	50	44
	Fourth	50	44
	Little	52	45

The following rules will be applied for the LDI calculation in case of unclear data.

- Circumferences of 0 will be considered as missing. Circumferences <15 will be assumed to be in cm instead of mm and will be multiplied by 10 before being used in summaries/analyses.
- If both digits of a given pair are recorded as affected, then each digit will be compared to the normative value (shown in the above table). Note that if both comparisons result in a difference $\geq 10\%$, then both digits will contribute to the final LDI score.
- If the circumference of the affected digit is smaller than the unaffected digit, then the LDI will be calculated by comparing the smaller digit to the normative value.
- If a digit is recorded as affected and the circumference of the contralateral digit is missing, the normative value will be used for comparison with the affected digit.
- If a digit is selected but recorded as 'not affected' but has circumference and contralateral circumferences collected, a missing tenderness score will be considered as 1.
- If the investigator did not complete the LDI questionnaire at Baseline, it will be assumed that no digits were affected (ie, a LDI score of 0 will be assigned).

Dactylitis-free state is based on a Leeds Dactylitis Index (LDI) at Week 16 of 0, for subjects with dactylitis at Baseline ($LDI>0$).

Dactylitis-free state at Week 16 (pooled between PA0010 and PA0011) is the 8th endpoint in the sequential testing hierarchy (Table 4–5) and will be based on pooled data from PA0010 and PA0011 (for subjects in the BKZ160mg Q4W and the Placebo groups). The analysis will also be repeated using PA0010 data alone and the p-value will only be considered nominal.

A tender dactylitis count will be calculated as the sum of the tenderness scores for all digits and will be used for the PASDAS score calculation (Section 8.3.1.6).

8.2.1.8 Psoriasis Area Severity index 90 (PASI90) at Week 4 (in subjects with PSO involving at least 3% of BSA at Baseline)

This variable will be derived as described in Section 8.2.1.2.

8.2.1.9 ACR20 and ACR70 response at Week 16

The ACR20 and ACR70 responses are defined based on respectively 20% and 70% or greater improvement from Baseline in the same measures than the primary endpoint (Section 8.1.1).

8.2.1.10 Proportion of subjects with an Investigator Global Assessment (IGA) score of 0 (clear) or 1 (almost clear) AND at least a 2-grade reduction from Baseline at Week 4 and Week 16 in the subset of subjects with psoriatic skin lesions at Baseline

A static IGA for PSO will be used to assess disease severity in all subjects during the study. The Investigator will assess the overall severity of PSO using the following 5-point scale presented in [Table 8-4](#).

Table 8-4: Five-point IGA

Score	Short Descriptor	Detailed Descriptor
0	Clear	No signs of PSO; post-inflammatory hyperpigmentation may be present
1	Almost Clear	No thickening; normal to pink coloration; no to minimal focal scaling
2	Mild	Just detectable to mild thickening; pink to light red coloration; predominantly fine scaling
3	Moderate	Clearly distinguishable to moderate thickening; dull to bright red, moderate scaling
4	Severe	Severe thickening with hard edges; bright to deep dark red coloration severe/coarse scaling covering almost all or all lesions

IGA=Investigator's Global Assessment; PSO=psoriasis

The IGA response is defined as clear [0] or almost clear [1] assessment with at least a 2-category improvement from Baseline, meaning that this parameter will be only evaluable for subjects with psoriatic skin lesions (IGA score ≥ 2) at Baseline.

Note that per protocol and device setting, only subjects with BSA $\geq 3\%$ at Baseline will have IGA assessed at post-Baseline visits.

For some subjects with BSA $\geq 3\%$ at Baseline, IGA data have not been captured at Week 4 and Week 16 visits when BSA $< 3\%$ at those visits. To address that, an additional supportive analysis will be performed in which these subjects will be considered as IGA responders at the respective visit.

8.2.1.11 Change from Baseline in the Patient's Assessment of Arthritis Pain (PtAAP) at Week 16

The change from Baseline at Week 16 in PtAAP will be analyzed as described in [Section 8.1.4.4](#).

8.2.1.12 Enthesitis-Free state based on Spondyloarthritis Research Consortium of Canada (SPARCC) index at Week 16

The SPARCC index measures the severity of enthesitis through the assessment of 16 sites, 8 for the right part and 8 for the left part of the body: the greater trochanter (right/left), quadriceps tendon insertion into the patella (right/left), patellar ligament insertion into the patella and tibial tuberosity (right/left), achilles tendon insertion (right/left), plantar fascia insertion (right/left), medial and lateral epicondyles (right/left), and the supraspinatus insertion (right/left). Tenderness on examination is recorded as either present (1) or absent (0) for each of the 16 sites, for an overall score range of 0 (no enthesitis) to 16 (severe enthesitis).

In case 9 or more are missing, the SPARCC index will be set to missing. If at least 8 items are available, the available items will be assessed and scored and then weighted by the number of the assessed items as shown in the formula below:

$$SPARCC\ index = n \times \frac{\sum_{i=1}^n score}{\sum_{i=1}^n AI}$$

where n refers to the number of total items and AI the number of assessed items.

The analysis of enthesitis-free state based on SPARCC index at Week 16 from Baseline will be restricted to the subset of subjects with enthesitis at Baseline (defined as SPARCC>0).

8.2.1.13 Change from Baseline in PsAID-12 total score at Week 16

The PsAID questionnaires measure the impact of disease on the subject. The impact of PsA is measured by weighting 12 different domains of health to derive a weighted summary score. The domains are pain, fatigue, skin problems, work and/or leisure activities, functional capacity, discomfort, sleep disturbance, coping, anxiety/fear/uncertainty, embarrassment and/or shame, social participation, and depression. The PsAID score is based on the relative importance of each of the domains. Each domain is answered based on a numeric rating scale ranging from 0 to 10.

The equation for the PsAID-12 score is as follows:

$$PsAID - 12 = \frac{1}{20} (3 \times Pain + 2 \times Fatigue + 2 \times Skin\ Problems + 2 \times Work/Leisure + 2 \times Functional\ Capacity + 2 \times Discomfort + 2 \times Sleep\ Disturbance + Coping + Anxiety/Fear + Embarrassment/Shame + Social\ Participation + Depression)$$

The total score also ranges from 0 to 10 with higher scores indicating a worse impact of the disease. A score below 4 out of 10 is considered a subject-acceptable status. A change of 3 or more points is considered relevant absolute change.

If a value (from the 12 domains) is missing, the missing value will be imputed in taking the mean value of the remaining (non-missing) domains, and the imputed value will be used to calculate the PsAID with the formula above. If 2 or more of the domains are missing, the PsAID score will be set to missing.

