MDA at Week 16 is the 5th endpoint in the sequential testing hierarchy ([Table 4-5](#)).

8.2.1.5 Van der Heijde modified Total Sharp Score (vdHmTSS): Change from Baseline at Week 16

The degree of joint damage is to be assessed using the vdHmTSS as used in the evaluation of PsA (Van der Heijde et al, 2005). This methodology quantifies the extent of joint erosions (52 joints) and joint space narrowing (52 joints), with higher scores representing greater damage.

Radiographs of the hands and feet are to be taken using standardized imaging methodology, which is defined in the Hand and Foot Radiography Manual that will be provided as part of the Study Manual.

All enrolled subjects are required to have radiographs taken of both hands and both feet (a single posteroanterior view of each hand and a single dorsoplantar of each foot). Radiographs are to be read centrally and independently by 2 experienced readers. If the 2 primary readers disagree, adjudication will be performed by a third reviewer. Readers will be blind to treatment assignment and time course of the films. Additional details on radiograph reading, assessment, and adjudication should be given in the imaging charter.

The scoring methodology is outlined below.

Scoring of Erosions:

Bone erosions in the hands and feet will be scored in the following locations according to the following grading scheme:

Erosion Scoring Locations:

- 20 locations in each hand and wrist (left and right): 40 locations overall:
 - 4 Distal inter-phalangeal joints (2-5)
 - 4 Proximal Inter-Phalangeal Joints (2-5)
 - 5 Metacarpo-Phalangeal Joints (1-5)
 - Inter-Phalangeal Joint of the thumb
 - Proximal first Metacarpal Bone
 - Radius Bone
 - Ulnar Bone
 - Trapezium and Trapezoid (as one unit; multangular)
 - Navicular Bone
 - Lunate Bone.
- 6 joints in each foot (left and right), 12 locations overall for the 2 feet:
 - 5 Metatarso-phalangeal joints (1-5)
 - Inter-phalangeal joint of the first toe.

Erosion Grading Scheme:

- Scores will be based on the number and size of discrete erosions in each location as follows:
 - 0=Normal (no erosion)
 - 1=Discrete small erosion
 - 2=Either 2 discrete erosions or 1 larger erosion that do not cross the joint middle line

- 3=Combination of the above or 1 large erosion that cross the joint middle line of the bone
- 4=Combination of above adding up to 4
- 5=Combination of above adding up to 5 or more.

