In the feet as for the hands/wrists the individual joint scores will be summed separately to create a total ES and a total JSN score for the feet.

- The maximum total ES for both feet is 120 (12 locations \times 10 per joint)
- The maximum total JSN score for both feet is 48 (6 locations \times 4 maximum per joint \times 2).

Thus, the maximum possible scores are:

- 320 for erosions
- 208 for joint space narrowing
- 528 for the total score.

The total score is the sum of the ES and JSN score.

Radiographic assessments should be conducted using a standardized imaging methodology as defined in an imaging charter. Subjects reaching Week 52 will have 2 sets of reads for Baseline and Week 16 as x-rays for these subjects are read more than once in different sessions to reduce within subject variability by each of the independent reviewers.

Bone erosions will be read for all visits at both at the Week 24 analysis and the Week 52/final analyses to ensure that unnecessary bias is not introduced. Given there may be differences at a visit for the two sets of reads, the following rules will be applied for the derivation:

- For the analysis involving data up to Week 16 only (Week 24 analysis), the first set of reads will be used for all subjects.
- For the analyses involving data up to Week 52, the second set of reads will be used for all subjects.

For the analysis, the average of the scores (ES, JSN score and total score) from the 2 independent reviewers will be utilized. They will be calculated as:

- $(\text{Score from Reviewer 1} + \text{Score from Reviewer 2})/2$

When a third reviewer will perform adjudication, the following average will be used for the scores:

- (Sum of the adjudicated score + score closest to the adjudicated score)/2

If the 2 scores are equidistant to the adjudicated score, then the highest score will be taken.

For the assessment of an individual reviewer, the following imputation rules will be applied:

- If at least 1 score for a particular joint used to calculate JSON score or ES at a visit is available, the remaining score will be imputed:
 - For Baseline, missing scores for a particular joint will be set to 0
 - At post-Baseline visits, missing score for a particular joint (ie, the assigned score is "N" or "S"), the joint score from the previous visit will be carried forward to compute the total score.

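### The adjudication rule for vdHmTSS (SAP 8.2.1.5) picks the primary reader score by score, so the total can differ from ES + JSN and reader offsets can add noise to the change tested in H6 and H9

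*SAP*

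**What the plan says.** All of this is in SAP section 8.2.1.5.

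- **Two readers:** "the average of the scores (ES, JSN score and total score) from the 2 independent reviewers will be utilized".
- **Trigger:** "If the 2 primary readers disagree, adjudication will be performed by a third reviewer". No threshold is given, and the text does not say whether disagreement is judged on a score, a visit or a change.
- **Adjudicated value:** "When a third reviewer will perform adjudication, the following average will be used for the scores". The formula, after its opening bracket, is "Sum of the adjudicated score + score closest to the adjudicated score)/2".
- **Ties:** "If the 2 scores are equidistant to the adjudicated score, then the highest score will be taken".
- **Total:** "The total score is the sum of the ES and JSN score".
- **Blinding:** "Readers will be blind to treatment assignment and time course of the films".
- **Charter:** "Additional details on radiograph reading, assessment, and adjudication should be given in the imaging charter".

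The change from Baseline in this score at Week 16 is tested as H6 (elevated hs-CRP and/or erosion) and H9 (all subjects). It also defines the no-progression responders in section 8.3.1.15 (change of at most 0.5).

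**The concern.** A plain two-reader mean is linear. ES and JSN add up to the total, and a stable difference in level between readers cancels in the change because the same two readers enter both visits. Picking the closest reader is not linear, so neither property is guaranteed once a film is adjudicated.

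Two things are at stake. First, two programmers could follow the SAP and obtain different vdHmTSS totals for the same subject. Second, a level difference between readers can appear as a change of a point or more, on an endpoint planned in H6 with a treatment difference of 0.30 and an SD of about 0.72.

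**Working it through.** **1. The plan's own power** (SAP 2.4.2; two-sided Satterthwaite t-test, alpha 0.05)

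- H6: 45% of 420 and 280 gives 189 and 126. SE = √(0.72²/189 + 0.71²/126) = 0.0821, and 0.30/0.0821 = 3.65. Power is 95.4% (stated 95%).
- H9: SE = √(1.13²/420 + 2.44²/280) = 0.1559, and 0.42/0.1559 = 2.69. Power is 76.6% (stated 76%).

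Both reproduce.

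**2. Total against ES + JSN** (hypothetical scores, one visit)

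| | Reader A | Reader B | Adjudicator | Closest | Result |
|---|---|---|---|---|---|
| ES | 10 | 4 | 9 | A | (9+10)/2 = 9.5 |
| JSN | 5 | 9 | 8 | B | (8+9)/2 = 8.5 |
| Total | 15 | 13 | 17 | A | (17+15)/2 = 16 |

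ES + JSN = 9.5 + 8.5 = 18, but the rule applied to the total gives 16.

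**3. Reader switch between visits** (hypothetical totals)

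Reader A scores 20 at both visits and reader B scores 24 at both. The adjudicator scores 21, then 23.

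- As written: (21+20)/2 = 20.5, then (23+24)/2 = 23.5. Change +3.0.
- Adjudicator and A at both visits: 20.5, then (23+20)/2 = 21.5. Change +1.0.
- Excess: 2.0 = (24−20)/2, half the difference between the primary readers.

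The tie rule is a second route. With the adjudicator at 21, then 22, the second visit ties and takes 24: (22+24)/2 = 23. The change is +2.5, against 21.0 − 20.5 = +0.5 with A held.

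**4. How often and how large** (assumptions, not SAP figures)

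One simulation set true change to zero, gave each reader a persistent offset (SD 1–3 per sub-score) and a visit error (SD 0.5–1.0), and adjudicated on any disagreement in the total. Among adjudicated subjects:

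- the closest reader switched between visits in 7–27%;
- 40–50% of totals differed from ES + JSN;
- the SD of change was 10–50% larger than with a fixed pair (for example 0.973 against 0.813, and 1.137 against 0.757);
- the mean false change was about 0 (−0.006 to 0.002).

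A simpler sensitivity adds a mean-zero false change of ±g points in a share q of subjects to the planning SDs, so the variance rises by q·g²:

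| q | g | SD (BKZ, H6) | H6 power | H9 power |
|---|---|---|---|---|
| 2% | 1 | 0.734 | 94.6% | 76.4% |
| 5% | 2 | 0.848 | 87.0% | 74.7% |
| 10% | 1 | 0.786 | 91.4% | 75.6% |
| 10% | 2 | 0.958 | 77.8% | 72.7% |

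**5. Dependence on the unstated trigger**

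This simulation of the total score assumes reader offset SD 1–3, reading error SD 0.7, true-change SD 0.35 and a 3-point trigger.

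| Unit of adjudication | SD of change | H6 power |
|---|---|---|
| Only the discordant visit, written rule | 0.93–1.49 | 80% to 41% |
| Both visits, written rule | 0.85–1.07 | 86% to 68% |
| Disagreement judged on change, written rule | 0.79–0.80 | about 90% |
| One fixed pair per subject | 0.80–0.82 | 89–90% |

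With offset SD 1 and reading error 0.5, even adjudication of single visits gives an SD of 0.72 and 95% power.

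**The case against.** The strongest defence is the imaging charter, to which the SAP sends further adjudication detail. The charter may define disagreement, say whether the adjudicator reads one film or the whole series, and fix the reader pair. That the choice is made separately at each visit is an inference, because the adjudication rule names no visit. This stands as a limit on how often the problem occurs. It does not clear the SAP, which writes out the formula and tie rule itself: a charter that fixes the pair would have to be reconciled with that text, and one that does not leaves the problem in place.

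On the total, it can be said that deriving it from the final ES and JSN gives 18 and no conflict. That is the sensible reading, but the averaging sentence lists the total alongside ES and JSN, so the other reading is equally literal.

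A reader might infer that H6 is badly underpowered. The documents do not support this. The largest losses in step 5 need an assumed 3-point trigger at a single visit and large reader offsets (57% of subjects are adjudicated at offset SD 3). Much of that loss comes from comparing an adjudicated visit with an unadjudicated one, not from picking the closest reader. If disagreement is judged on change, the loss vanishes, and the step 3 example, where both primary readers see no change, would not be adjudicated. The planning SDs may also already contain reading noise.

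A reader might also infer that the higher-score tie rule biases progression upward. It raises whichever visit ties, Baseline or Week 16, and readers know neither treatment nor time order. No bias toward an arm is shown.

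**Conclusion.** The point holds as a defect in a derivation rule. The conflict between the rule and the definition of the total follows from the text alone and needs no assumption about readers. That a reader switch puts half the difference between the primary readers into the change also follows from the formula, provided both visits are adjudicated without a fixed pair.

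The consequence is lost precision in H6, H9 and the no-progression classification. The SAP gives no reader variance, adjudication rate, threshold or unit, so the size cannot be derived from it; the ranges in steps 4 and 5 are sensitivities only, from no visible loss to a substantial one. The stated powers are correct for their inputs. The rule should be changed because a better one is available at little cost.

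**What to change.** For an adjudicated subject:

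- Select the primary reader once per subject and read set, by a prespecified criterion applied blind to treatment. One choice is the reader whose change in total score is closest to the adjudicator's. In the step 4 simulation, this and the smallest summed distance over both visits each gave a smaller SD of change than the written rule.
- Use the adjudicator and that reader at all visits of the read set, for both ES and JSN.
- Replace the higher-score tie rule with a symmetric one, such as the mean of the two primary readers.
- Derive the total only as ES + JSN, and remove it from the list of separately averaged scores.
- State the trigger and unit of adjudication, or cite where the charter states them, and make the two documents agree.

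The cost is a few lines of SAP text, reprogramming of one derivation and alignment with the charter. The adjudicator must score every visit of an adjudicated subject, if that is not already done. If the Week 24 results are already unblinded, report the corrected rule for the first read set as a sensitivity analysis beside the one that was specified.

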Injected joints are allowed after Week 16 as part of rescue medications.

Dactylitic digits will be identified as follows and the joints will be counted as follows:

- Fingers 2-5: Swelling Distal Interphalangeal Joint x (side), Swelling Proximal Interphalangeal Joint x (side), Swelling Metacarpophalangeal Joint x (side) – if they are in any of the gradings ‘swollen only’ or ‘tender and swelling’ or ‘injected’ then only 1 finger will be added to the swollen joint count.
- Toes 1-5: Swelling Interphalangeal Joint x (side), Swelling Metatarsophalangeal Joint x (side) – if they were in any of gradings ‘swollen’ or ‘tender and swollen’ or ‘injected’ then only 1 toe will be added to the swollen joint count.

The tender joint count (TJC) and swollen joint count (SJC) are weighted joint counts. If there are missing observations in the tender or swollen joint assessments (TJ and SJ, respectively), then the remaining observations will be assessed and weighted by the number of the assessed joints (AJ) as shown below:

$$TJC = n \times \frac{\sum_{i=1}^n TJ}{\sum_{i=1}^n AJ}$$

$$SJC = n \times \frac{\sum_{i=1}^n SJ}{\sum_{i=1}^n AJ}$$

Where n represents the number of total joints.

If a joint is missing at Baseline, then that joint is set to missing throughout the study. If more than 50% of the planned tender joint assessments (ie more than 34) or 50% of the planned swollen joint assessments (ie more than 33) are missing at the time of a given assessment any post-Baseline visit, then no imputation will be done and the total TJC or SJC will be set to missing for that visit.

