The maximum score for erosion is 5 per joint in the hand and 10 per joint in the feet.

A score of "N" will be assigned in the case that the location is non-evaluable due to advanced subluxation, interfering osteoarthritis, or poor radiographic depiction. A score of "S" will be assigned in the case that the location had joint replacement, amputation, or other surgery. Exported score will be from 0 to 5 for hand and 0 to 10 for foot. Score of "S" and "N" will not be exported as a score but in an additional text field ("Reason").

Scoring of Joint Space Narrowing:

Joint space narrowing (JSN) in the hands and feet will be scored in the following locations according to the following grading scheme:

Joint Space Narrowing Scoring Locations:

- 20 locations in each hand and wrist (40 locations overall):
 - 4 Distal inter-phalangeal joints (2-5)
 - 5 Metacarpo-phalangeal joints (1-5)
 - 4 Proximal inter-phalangeal joints (2-5)
 - Interphalangeal Joint of thumb (IP)
 - 3 Carpo-metacarpal joints (3-5)
 - Radio-carpal joint
 - Multangular-navicular joint
 - Capitate-navicular-lunate joint.
- 6 locations in each foot (12 locations overall):
 - 5 Metatarso-phalangeal joints
 - Inter-phalangeal joint of first toe.

Joint Space Narrowing Grading Scheme:

- The joints mentioned above will be scored using a 5-point scale from 0 to 4 as follows:
 - 0=normal
 - 1=asymmetrical or minimal narrowing up to a maximum of 25%
 - 2=definite narrowing with loss of up to 50% of the normal space
 - 3=definite narrowing with loss of 50–99% of the normal space or subluxation
 - 4=absence of a joint space, presumptive evidence of ankylosis, or complete luxation.

A score of "N" will be assigned in the case that the location is non-evaluable due to advanced subluxation, interfering osteoarthritis, or poor radiographic depiction. A score of "S" will be assigned in the case that the location had joint replacement, amputation, or other surgery. Exported score will be from 0 to 5 for hand and 0 to 10 for foot. Score of "S" and "N" will not be exported as a score but in an additional text field ("Reason").

Total Scores:

The individual joint scores will be summed separately to create a total erosion score (ES) and a total JSN score for the hands/wrists.

- The maximum total ES for both hands/wrists is 200 (20 locations \times 5 maximum per joint \times 2).
- The maximum total JSN score for both hands/wrists is 160 (20 locations \times 4 maximum per joint \times 2).

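### vdHmTSS: a joint unreadable at Baseline is scored 0, so if it later reads above 0 its whole score counts as progression; this adds noise, mainly to H6, but does not bias the treatment comparison

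*SAP*

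**What the plan says.** SAP section 8.2.1.5 gives two rules for a joint that an individual reader could not score:

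- Baseline: "For Baseline, missing scores for a particular joint will be set to 0".
- After Baseline, where the joint is marked N or S: "the joint score from the previous visit will be carried forward to compute the total score".

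N marks a location that is "non-evaluable due to advanced subluxation, interfering osteoarthritis, or poor radiographic depiction". S marks joint replacement, amputation or other surgery. On both the erosion and the narrowing scale, 0 is the normal grade. On the range of the erosion scale: "The maximum score for erosion is 5 per joint in the hand and 10 per joint in the feet". Narrowing runs from 0 to 4.

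Joint scores are summed for each reader, and then "the average of the scores (ES, JSN score and total score) from the 2 independent reviewers will be utilized". If a third reader adjudicates, the adjudicated score is averaged with the closer of the other two. On blinding: "Readers will be blind to treatment assignment and time course of the films".

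The change from Baseline to Week 16 is tested twice in the hierarchy (section 4.5, Table 4-5): H6 in subjects with elevated hs-CRP and/or erosion, and H9 overall. A change of at most 0.5 defines non-progression (section 8.3.1.15), which is outside the hierarchy.

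For tender and swollen joint counts, section 8.1.1.1 has a different rule: "If a joint is missing at Baseline, then that joint is set to missing throughout the study".

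**The concern.** The Baseline rule treats a joint that could not be read as a joint without damage. If the later film can be read and shows damage, the subtraction treats all of it as new, although it may have been there at entry.

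The true changes are small. Section 2.4.2 assumes mean changes of 0.06 and 0.36 for H6. A single joint moving from a rule-made 0 to a real 2 is large against those values. H6 also gates H7 to H9, so power lost at H6 is passed down the sequence.

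Nothing else in the SAP offsets the rule. Multiple imputation, the observed-case analysis and the analysis excluding subjects with fewer than 2 radiographs all deal with missing totals or missing films. The Radiographic Set (section 3.6.9) requires a valid Screening image, not a readable score in every joint. No sensitivity analysis of the joint-level rule is planned.

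**Working it through.** **Step 1: what the rules do to one joint, for one reader**

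| Baseline | Week 16 | Contribution to change |
|---|---|---|
| N, set to 0 | reads k > 0 | +k, no change observed |
| N, set to 0 | reads 0 | 0 |
| N or S, set to 0 | N or S, 0 carried forward | 0 |
| reads k | N, k carried forward | 0 |

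Only the first row creates an artefact, and it is always upward. It needs a joint that becomes readable, so the main source is poor depiction at Baseline.

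**Step 2: size in the averaged score.** With k = 2, the artefact is (2 + 2)/2 = 2 if both readers marked N at Baseline. It is (2 + 0)/2 = 1 if only one did, the other saw no change and there was no adjudication. With no other change, either value exceeds the 0.5 cut-off. With k = 1 and one reader affected, the result is exactly 0.5, which still counts as non-progression.

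**Step 3: reproduce the plan's power.** Inputs from sections 2.4.1 and 2.4.2: 420 and 280 subjects, two-sided alpha 0.05, Satterthwaite t-test.

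- H6: n = 0.45 × 420 = 189 and 0.45 × 280 = 126; difference 0.30; SD 0.72 and 0.71. SE = √(0.72²/189 + 0.71²/126) = 0.0821; noncentrality 0.30/0.0821 = 3.65; power 95.4% (SAP: 95%).
- H9: n = 420 and 280; difference 0.42; SD 1.13 and 2.44. SE = 0.1559; noncentrality 2.69; power 76.6% (SAP: 76%).

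The plan's power figures are correct as calculated.

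**Step 4: add the artefact.** Let a share q of subjects in each arm gain a points in the reader-averaged score. Both q and a are assumptions, because the SAP gives neither. The mean change rises by qa in each arm, the expected difference is unchanged, and each arm's variance rises by q(1−q)a².

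Example, q = 0.05 and a = 2: added variance 0.05 × 0.95 × 4 = 0.19; SDs √(0.5184 + 0.19) = 0.842 and √(0.5041 + 0.19) = 0.833; SE 0.0962; H6 power 87.4%.

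| q | a | Mean shift, each arm | H6 power | H9 power |
|---|---|---|---|---|
| none | none | 0 | 95.4% | 76.6% |
| 1% | 1 | 0.01 | 95.0% | 76.5% |
| 1% | 2 | 0.02 | 93.9% | 76.2% |
| 2% | 1 | 0.02 | 94.7% | 76.4% |
| 2% | 2 | 0.04 | 92.3% | 75.9% |
| 2% | 3 | 0.06 | 88.1% | 74.9% |
| 5% | 1 | 0.05 | 93.6% | 76.2% |
| 5% | 2 | 0.10 | 87.4% | 74.8% |
| 5% | 3 | 0.15 | 76.6% | 72.5% |

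The rows with a = 1 correspond to one affected reader and a joint score of 2.

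**The case against.** **No bias between arms.** A reader might infer that false progression distorts the bimekizumab-placebo difference or inflates type I error. The documents do not support that. Allocation is randomised, and readers know neither the arm nor the order of the films, so the artefact falls equally on both arms in expectation. This stands in full; what is left is noise and an inflated level.

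**The mechanism is narrow.** It is tempting to say that any later readable score counts as damage. It does not: a later 0 adds nothing, and joints that stay N or S add nothing. Nor do the joint rules taken together err only upward, because carrying a score forward can hide real progression. This stands.

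**The size is assumed.** The larger losses need both readers to mark N and a score of 2 or 3. The H6 SDs come from another trial's results and may already contain similar noise. The imaging charter, not shown, may make such joints rare. This stands and is why only a range is given.

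**The wording is conditional.** The rule is introduced by a requirement that at least one score for the joint be available. Read narrowly, that covers a joint scored for erosion but not narrowing, or the reverse, and does not clearly cover a joint with no score at all. The condition is loose. On the narrow reading the artefact still arises in partly scored joints, and the post-Baseline bullet itself equates a missing joint score with N or S.

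**The joint counts are a different instrument.** They drop the joint and reweight, whereas vdHmTSS is a plain sum, and elsewhere the SAP sets missing items to 0 (mNAPSI). So section 8.1.1.1 does not contradict section 8.2.1.5. It shows only that the SAP handles the same problem differently elsewhere.

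**Conclusion.** The concern holds in limited form. Followed as written, the Baseline rule gives a wrong change from Baseline for a subject whose joint goes from unreadable to a score above 0, and no other part of the SAP corrects it. The consequences are higher mean progression in both arms, extra variance and misclassified progressors.

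Under the assumed 1% to 5% of subjects and 1 to 3 points, with the artefact equal in both arms, H6 power lies between 95.0% and 76.6% against 95.4% without it. At 1 point it lies between 95.0% and 93.6%. H9 lies between 76.5% and 72.5% against 76.6%, so naming H6 and H9 as equally exposed would overstate the case. If such joints are rare, the loss is negligible. The true frequency cannot be judged from the SAP.

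**What to change.** In section 8.2.1.5, replace the Baseline rule for the change-from-Baseline analyses. For each reader, a joint scored N or S at Baseline is left out of that reader's erosion or narrowing total at all visits. No reweighting is needed. Leaving a joint out of a sum equals scoring it 0, so Baseline totals, and with them the ANCOVA covariate, stay as they are; only later totals change. Clarify the introductory condition so that it is plain whether a joint with no score at all is covered.

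Keep the set-to-0 rule as a sensitivity analysis for H6, H9 and the non-progression endpoint, and report by arm how many joints and subjects are affected.

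Do not fill Baseline from a later film: that would put post-randomisation data into the Baseline covariate.

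The cost is SAP wording and a change to one derivation, using the reason field already exported with the scores. The downside is small: real new damage in a joint unreadable at Baseline is not counted.
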